#### Gene expression analysis

A fraction of the liver tissue collected during biopsy will be used to conduct gene expression analysis (refer to Liver biopsy in the [Flow Chart](#)). For any liver biopsies conducted during the trial, the generation of slides for the histological staging of NASH will take precedence over sample collection for gene expression analysis. For further details refer to [Section 5.5.3](#).

### 5.1.2 Fibroscan Assessment of Liver Stiffness [REDACTED]

The liver will be evaluated using the FibroScan® device, a non-invasive technique using Vibration Controlled Transient Elastography (VCTE™) technology (to measure liver stiffness) [REDACTED]

The following measurements will be made:

- Fibrosis will be measured using Vibration-Controlled Transient Elastography (VCTE) which is an advanced ultrasound technique that measures liver stiffness.

[REDACTED]

Sites must have the expertise in using the FibroScan® device, i.e., the operator should be duly trained. If possible, the same operator should perform the Fibroscan® assessments on one patient.

Correct probes should be selected corresponding to the patient's body type (follow the automatic probe selection tool displayed in real time, based on the Skin to Liver Capsule Distance (SCD), and not on patient's BMI). Sites should ensure that the probes are calibrated.

If the FibroScan® device is not available at the site, it will be provided by the Sponsor for the duration of the trial.

### 5.1.3 Magnetic resonance imaging

MR imaging will be used to assess the liver fat content in the whole liver by way of proton density fat fraction (PDFF) at the time points specified in the Flow Chart. Therefore, sites must be equipped or collaborating with a site equipped with an MRI scanner from the following manufacturers: General Electric, Philips or Siemens. Ideally the MRI scanner should be equipped with a manufacturer specific MRI-PDFF package also known as multi-echo, multi-peak Dixon techniques. All imaging sites will undergo a quality assessment process prior to trial initiation based on a review of MRI hardware and software.

MR images to compute the whole liver volume (by way of 3D image acquisition) will also be collected from each subject in the same MRI session in order to compute the liver fat volume. Other MR image sequences may be collected for additional exploratory analyses if required. MR image acquisition, including preparation time, is estimated to take no longer than 30 minutes. MR images will be sent to an external vendor for centralized reading.

### 5.1.4 Weight

Weight measurements should always be done on the same scales for one patient whenever possible. Mechanical and digital scales are acceptable. In order to get comparable body weight values, shoes, coats/jackets, and any headgear should be taken off, and pockets should be emptied of heavy objects (i.e., keys, coins etc.). Headgear worn for religious reasons are

acceptable, but this should be worn for all weight measurements in the trial. The patient should empty the bladder before weight is measured.

### 5.1.5 Waist and hip circumference

Waist circumference should be determined by measuring the midpoint between the lowest rib and the iliac crest. The measuring tape should be made of a material that is not easily stretched. The tape should be placed perpendicular to the long axis of the body and horizontal to the floor and applied with sufficient tension to conform to the measurement surface. Waist circumference measurements should be made around a patient's bare midriff, after the patient exhales while standing without shoes and with both feet touching the ground and arms hanging freely.

Hip circumference measurement should be taken around the widest portion of the buttocks.

## 5.2 ASSESSMENT OF SAFETY

### 5.2.1 Physical examination

A complete physical examination will be performed at the screening visit. Further physical examinations during the trial are required only if patient reports symptoms (please refer to in the [Flow Chart](#)). The physical examination should be conducted according to the local medical practice. It includes at a minimum general appearance, neck, lungs, cardiovascular system, abdomen, extremities, and skin.

Measurement of height and body weight will be performed at the time points specified in the Flow Chart. The results must be included in the source documents available at the site.

### 5.2.2 Vital signs

Vital signs will be assessed at the time points specified in the Flow Chart, prior to blood sampling. Blood pressure will be measured twice at Visit 1 (10 minutes apart). Vital signs measurement at Visit 1a is optional but recommended. At dosing visits another vital signs assessment will be done approx. 10 minutes post dose (i.e., after the administration of the second of two pre-filled syringes). Vital signs assessment consists of systolic and diastolic blood pressure and pulse rate (electronically or by palpation count for 1 minute) in a seated position without crossed legs, after 5 minutes of rest. The results must be included in the source documents available at the site.

### 5.2.3 Safety laboratory parameters

Safety laboratory parameters to be assessed are listed in [Table 5.2.3: 1](#). For the sampling time points please see the [Flow Chart](#). Patients do not have to be fasted for the blood sampling for the safety laboratory.

Analyses will be performed by a central laboratory; the respective reference ranges will be provided in the ISF. Instructions regarding sample collection, sample handling/ processing and sample shipping are provided in the laboratory manual.

The central laboratory will send reports to the Investigator. It is the responsibility of the Investigator to evaluate the laboratory reports. Clinically relevant abnormal findings as judged by the Investigator will be reported as AEs (please refer to [Section 5.2.6](#)).

In case the criteria for hepatic injury are fulfilled, a number of additional measures will be performed (please see [Section 5.2.6.1](#)) and the DILI Checklist provided in the ISF. The amount of blood taken from the patient concerned will be increased due to this additional sampling.

The central laboratory will transfer the laboratory data to the Sponsor periodically.

Table 5.2.3:1 Safety laboratory tests

Category	Test name
Haematology	Haematocrit Hemoglobin MCV (Mean Corpuscular Volume) MCH (Mean Corpuscular Haemoglobin) MCHC (Mean Cellular Haemoglobin Concentration) Red Blood Cell Distribution Width (RDW) Red Blood Cells (RBC) Count/ Erythrocytes WBC Count/ Leukocytes Platelet Count / Thrombocytes Differential Automatic (relative and absolute count): Neutrophils, Eosinophils, Basophils, Monocytes, Lymphocytes
Clinical chemistry	Albumin Alkaline phosphatase Amylase ALT (alanine aminotransaminase, SGPT) AST (aspartate aminotransaminase, SGOT) Bicarbonate Bilirubin total, fractionated if increased Calcium
Clinical chemistry	Chloride Creatinine Creatine kinase (CK) CK-MB, troponin (reflex tests if CK is elevated) Ferritin $\gamma$ -GT (gamma-glutamyl transferase) Glucose (plasma, not fasted) HbA1c/ Insulin/ C-Peptide** Lactate dehydrogenase (LDH) Lipase Magnesium Phosphate Serum Free Fatty Acids Potassium Protein total Sodium Urea (blood urea nitrogen, BUN) Uric acid Thyroid stimulating hormone (TSH)* Calcitonin* eGFR (CKD-EPI formula)
Coagulation	Activated Partial Thromboplastin Time (aPTT) Prothrombin Time (INR) Fibrinogen
Lipids	Cholesterol (total) HDL cholesterol LDL cholesterol (including VLDL) Triglycerides

Table 5.2.3:1 Safety laboratory tests (cont.)

Infectious serology	Hepatitis B surface antigen (HBsAg)* Hepatitis B surface antibodies (anti-HBs)* Total hepatitis B core antibodies (anti-HBs)* Hepatitis C antibodies (anti-HCV)*
Urinalysis	Semi quantitative Nitrite Protein Ketone Urine pH Leukocyte esterase (for WBC) Blood (erythrocytes)  Quantitative*** Albumin Creatinine  Urine drug screen* Cannabis Cocaine Benzodiazepine Amphetamines Barbiturates Methadone Opiates

\* Measured only at Visit 1.

\*\* Measured only at Visit 1, Visit 2, Visit 27 and at the EOT/ED visit.

\*\*\* Albumin/creatinine ratio in spot urine will be calculated at the central laboratory.

SARS-CoV-2 RT PCR test will be performed at Visit 1.

ADAs, NABs, level of BI 456906, IgE, histamine, serum tryptase, and complement components will be analyzed in the event of systemic hypersensitivity.

If the assessment of safety laboratory tests in the central laboratory is not possible due to emergency, pandemic or other unforeseen circumstances, the assessment will be performed in the local laboratories.

#### 5.2.4 Electrocardiogram

The 12-lead ECG should be collected at the time points specified in the [Flow Chart](#). ECG will be recorded in triplicate at the screening visit, but as a single measurement at the following visits.

Centralized ECG services will be provided by an external vendor for all site visits (including unscheduled visits). Standardized equipment and user manual will be provided by the vendor.

ECG should be collected according to the trial-specific recommendations, using the standardized equipment provided by the vendor. ECGs may be repeated for quality or safety reasons. Patients should be supine for approximately 5-10 minutes before ECG collection. Patients should remain supine, but awake, during the ECG collection process.

ECG recordings will be transmitted electronically to a vendor for central reading. The ECG recordings will be centrally evaluated and rated as normal, abnormal, or unable to evaluate, and the results will be sent to the site. The Investigator should review the report. If the ECG is rated as abnormal, the Investigator will have to determine if the abnormal findings are clinically significant. The Investigator will have the responsibility to follow up with the patient if there are any clinically significant findings in the ECG report.

After the screening visit, the Investigator must review the ECG results from central reading to ensure patient has met all the entry criteria for the trial. Any pre-existing conditions should be recorded as baseline conditions. ECG recorded at the randomization visit should be evaluated by the Investigator before the patient receives the first dose of trial medication. If abnormalities are observed by the Investigator in the ECG reading at randomization visit, the Investigator may wait until the results from central reading are available, and the randomization visit may be rescheduled.

After the patient is randomised, if a clinically significant increase in the QT/QTc interval from baseline or any other clinically significant quantitative or qualitative change from baseline is identified, the Investigator will assess the symptoms (e.g., palpitations, near syncope, and syncope) and decide if the patient will continue in the trial. The Investigator must also ensure that patient does not meet any of the stopping criteria, such as tachycardia, arrhythmia or conduction disorders ([Section 3.3.4.1](#)). Any new findings or deterioration of previous findings observed during the trial will be recorded as AEs or SAEs and should be followed up and/or treated as medically appropriate per local standards.

Although the ECGs are transmitted to the vendor for central reading, the Investigator has the responsibility to complete an initial review as soon as the ECG recordings are obtained at the site visit. At any time during the trial, the Investigator may decide to place a hold on further dosing of the patient if there is an indication of significant abnormalities in the ECG and would prefer to wait until the results from the central reading are available.

All ECGs that are read in the central location will be stored in the vendor's database and will be transmitted to the Sponsor periodically.

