### 3.3.4.1 Discontinuation of trial treatment

An individual patient will discontinue trial treatment if:

- The patient wants to discontinue trial treatment, without the need to justify the decision.
- An AE (CTCAE Grade 3 or higher) occurred, and the AE was assessed by the Investigator as related to the trial treatment ([Section 5.2.6.1.6](#) and [5.2.6.1.7](#)).
- A clinically significant laboratory change or abnormality occurred and the Investigator judges to warrant discontinuation of trial treatment.
- The patient develops a sinus tachycardia (HR >120/min in two consecutive measurements 5 minutes apart and/or tachyarrhythmia (HR >110/min) or cardiac condition requiring medical intervention.
- Ventricular tachycardia is seen on ECG or syncope.
- Clinically relevant changes are seen on the ECG (QTcF prolongation >500 ms or an increase of 60 ms from baseline (Visit 2), or Type Mobitz II, or third-degree AV block, or Torsade de Pointes) or the patient develops any symptomatic AV block, atrial fibrillation or atrial flutter requiring medical intervention.
- The patient develops a clinically relevant coronary artery disease (e.g., CCS grading of Angina pectoris grade III-IV, or congestive heart failure NYHA class III-IV, or any major adverse cardiovascular event)
- Signs of suicidal behaviour or ideation are detected.
- The patient develops a malignant neoplasm.
- The patient experiences systemic hypersensitivity. Refer to [Section 4.2.1](#).
- The patient develops a clinically significant elevation of liver enzymes. Refer to [Section 10.1](#).
- The patient experiences an infection with SARS-CoV-2 (as confirmed by RT-PCR test) and presents with signs or symptoms requiring discontinuation of trial treatment as per Investigator's discretion.
- The patient has repeatedly shown to be non-compliant with important trial procedures and, in the opinion of both, the Investigator and Sponsor representative, is not willing or able to adhere to the trial requirements in the future.
- The patient needs to take concomitant medication that interferes with the trial treatment for more than 2 weeks. Refer to [Section 4.2.2.1](#) and [4.2.2.2](#).
- The patient experiences tolerance issues with the dose due to AEs over 2 weeks within the treatment period before Visit 14 ([Section 4.1.2](#)).
- The patient is out of compliance with trial medication (missing doses), please see [Section 4.3](#).

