5.4 OTHER VARIABLE(S)

5.4.1 Safety

Safety will be assessed based on:

- Adverse events
 - Routine reporting using the Medical Dictionary for Regulatory Agencies (MedDRA) coding dictionary (version in force at final DBL)
 - Adverse events of special interest (AESIs)
 - Adjudicated adverse events
- Laboratory variables
 - Specific laboratory tests are listed in CTP Table 5.2.3: 1
- Vital signs
 - Pulse rate
 - Systolic blood pressure
 - Diastolic blood pressure

- 12-lead ECG

Further details regarding 12-lead ECG derivations are given below.

- Columbia - Suicide Severity Rating Scale (C-SSRS)

Laboratory data

Estimated glomerular filtration rate (eGFR) and urine albumin/creatinine ratio (UACR) will be used as provided by the central laboratory, i.e. it will not be re-derived for analysis.

Fib-4 index and APRI will also be used as provided by the central laboratory.

12-lead ECG

Single digital ECG recordings are planned to be collected at each relevant visit with the exception of screening, where triplicate ECG recordings are planned. Each of the recorded single ECGs will then be evaluated for cardiac intervals, which comprise the RR, PR and QT interval and the QRS duration. Measurements of these intervals will be made on four cardiac cycles from the lead chosen (details not specified here).

The measurements of the cardiac cycles will be stored in the database, i.e. four values per visit (for a single ECG). The four cardiac cycles (or however many available) will be averaged, to give a single mean value for each visit. This will be done prior to the calculation below of the heart rate (HR) and heart rate corrected QT interval (QTc).

For screening only, where a triplicate ECG is expected, the mean values obtained for each single ECG will be further averaged across the 3 ECGs (or however many available) to give a single mean value for each variable at screening.

The heart rate will be derived from the RR interval as:

$$\text{HR [beats/min]} = \frac{60\,000}{\overline{RR}}$$

where \overline{RR} is the mean of the four RR intervals (measured in msec).

The QT interval corrected for HR according to Fridericia's formula (QTcF) for a single ECG will be derived as:

$$\overline{QTcF} [\text{msec}] = \left(\frac{1000}{\overline{RR}} \right)^{1/3} * \overline{QT} [\text{msec}],$$

[figure not shown]

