6.7 BASELINE, TIME WINDOWS AND CALCULATED VISITS

Definition of baseline

In general, baseline is defined as the last non-missing measurement on or prior to the first administration of study medication. In the case that the first dose of study medication is delayed beyond the date of randomisation, a post-randomisation value can be used as a baseline value provided that it meets the stated requirement.

Where clock times are available (expected to include laboratory safety data, 12-lead ECG, plasma Survodutide concentrations and biomarkers) they will be used in addition to dates to define baseline, since it is also expected that the time of first study drug administration will be accurately recorded on the eCRF for all patients.

Unscheduled and repeat assessments are eligible for use as baseline values provided that they meet the above criterion.

For 12-lead ECG, if a screening value needs to be used for baseline, it will be the average of all available triplicate screening ECG measurements (see [Section 5.4.1](#) for derivation details).

For vital signs, the baseline definition will make the additional requirement that the data records are pre-dose. In practice, this will also be done using the clock times as well as the date. A single pre-dose measurement is expected to be captured at the baseline visit (Visit 2), which will therefore be used as baseline. In any situation in which only a post-dose measurement is available at Visit 2 and no pre-dose measurements, Visit 2 will not be used as baseline; the screening visit (Visit 1) will be used as baseline instead.

For baseline NAS and fibrosis scores, the following specific considerations will be applied:

- Either a biopsy performed during the screening period or a historical biopsy (within 6 months) will be used to provide baseline data, without any further distinction made for analysis purposes between these two situations (both referred to subsequently as “screening biopsy”).
- The baseline value will be derived from central pathology readings of screening biopsy slides. For sites in all countries except China, central pathology screening readings will always be physical readings. For sites in China, central pathology screening readings may be digital readings, the handling of which is described below.
- All adequate central pathology readings which meet the baseline definition will be used, including any (expected to be occasional) readings performed by the back-up

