7.8.4 ECG

Abnormal findings will be reported as baseline conditions (at screening) or as AEs (during the trial) if judged clinically relevant by the investigator.

The ECG recordings will be centrally evaluated and rated as normal, abnormal, or not evaluable.

All derivations relating to 12-lead ECG variables are given in [Section 5.4.1](#).

Occurrences of values above thresholds will be flagged in the listings. For QTcB and RR, only listings will be provided.

Quantitative variables

Descriptive statistics will be presented over time for absolute values and absolute changes from baseline in the following quantitative ECG variables: QTcF, HR, QT, QRS, PR.

Graphical summaries over time will also be included.

Categorical variables

Frequency tables will be provided for the categorical variables described below, which are determined from the specified quantitative ECG variables:

- New onset (meaning that this or a higher category was not present any time at baseline) of maximum QTcF interval > 450 to 480 msec, > 480 to 500 msec, or > 500 msec on treatment.
- New onset (not present any time at baseline) of uncorrected QT interval > 500 msec at any time on treatment
- Maximum change from baseline of QTcF ≤ 30 msec, > 30 to ≤ 60 msec, or > 60 msec on treatment.
- Maximum change from baseline of QT ≤ 60 msec, or > 60 msec on treatment.

For assignment of a particular patient to one of the above categories, all available time points on-treatment will be considered.

The occurrence of any of the following will be considered as “notable findings” and summarised using frequency tables:

- New onset (not present any time at baseline) of uncorrected QT interval > 500 msec at any time on treatment
- New onset of QTcF interval > 500 msec at any time on treatment
- Change from baseline of QTcF > 60 msec at any time on treatment
- Percentage change from baseline of HR $\geq 25\%$, when corresponding on-treatment value of HR is > 100 beats/min, or percentage change from baseline of HR $\leq -25\%$, when corresponding on-treatment value of HR is < 50 beats/min, at any time on-treatment
- Percentage change from baseline of PR $\geq 25\%$, when corresponding on-treatment value of PR interval is > 200 msec, at any time on treatment
- Percentage change from baseline of QRS $\geq 10\%$, when corresponding on-treatment value of QRS duration is > 110 msec, at any time on treatment.

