Frequency tables will also include morphological findings (determined and categorized based on SDTM terminology) that might be attributable to treatment. In particular, new onsets of findings not present at baseline will be explored. A morphological finding observed on treatment that was not reported at baseline will be categorized as a ‘new onset’ of this finding.

For all patients with any notable finding in ECG intervals, a separate listing will be created as end-of-text display, and the corresponding time profiles will be shown.

A shift table will be produced for QTcF, summarising the shifts from baseline to the maximum value on treatment, and displaying categories “ ≤ 450 msec”, “> 450 to 480 msec”, “> 480 to 500 msec and “> 500 msec”.

A scatter plot of QTcF at baseline and the maximum change from baseline (based on all on-treatment values as defined in [Section 6.1.6](#), and the maximum evaluated regardless of whether these were selected based on visit windows described in [Section 6.7](#)) will be produced. The plot will include diagonal reference lines for absolute QTcF equal to 450 msec, 480 msec and 500 msec, as well as horizontal reference lines for QTcF maximum changes from baseline equal to 30 msec and 60 msec.

Appropriateness of heart rate correction methods of QT interval

To evaluate the appropriateness of the heart rate correction methods, the slope of the relationship of the (untransformed) QTcF interval versus RR interval will be estimated for off-drug values and for each Survodutide maintenance dose group separately by applying a random coefficient (random slope and intercept) model. Off-drug values for this purpose are defined as only values (either baseline or on-treatment values as defined in [Section 6.1.6](#)) from patients randomised to placebo, since patients randomised to Survodutide dose groups are expected to have a single ECG at baseline only, and therefore cannot contribute a slope for estimation of an off-drug random effect for this. For the Survodutide maintenance dose group analyses, only on-treatment values will be used, and these will be included regardless of Survodutide dose (i.e. data from the dose escalation period will be included). The model will be fitted using the QTcF and RR pairs at each time point, using all values within the visit windows defined in [Section 6.7](#). A scatter plot of QTcF versus RR will be produced, and will

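### The single Visit 2 ECG is the baseline for ECG changes and the Visit 1 triplicate is set aside, so changes are noisier than the collected data allow, which dilutes but does not bias the comparison with placebo

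*Protocol*

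**What the plan says.** The two documents agree on how ECGs are recorded. Protocol 5.2.4 says "ECG will be recorded in triplicate at the screening visit, but as a single measurement at the following visits", and SAP 5.4.1 says "Single digital ECG recordings are planned to be collected at each relevant visit with the exception of screening, where triplicate ECG recordings are planned". Within one ECG, "The four cardiac cycles (or however many available) will be averaged, to give a single mean value for each visit".

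SAP 6.7 sets the general rule: "baseline is defined as the last non-missing measurement on or prior to the first administration of study medication". When a Visit 2 pre-dose ECG exists, that one recording is the baseline. The triplicate has a reserve role: "if a screening value needs to be used for baseline, it will be the average of all available triplicate screening ECG measurements". SAP 7.8.4 confirms the expectation in its section on heart rate correction: "patients randomised to Survodutide dose groups are expected to have a single ECG at baseline only".

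This baseline feeds the summaries of change in QTcF, HR, QT, QRS and PR in SAP 7.8.4, the maximum-change categories (for QTcF, cut at 30 and 60 ms) and the change-based notable findings. For the categories, "For assignment of a particular patient to one of the above categories, all available time points on-treatment will be considered". The protocol flow chart schedules 15 post-baseline ECGs, at Weeks 2, 4, 6, 8, 10, 12, 16, 20, 24, 28, 32, 36, 40, 44 and 48.

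Protocol 3.3.4.1 also ties its QTcF discontinuation criterion to that visit: "QTcF prolongation >500 ms or an increase of 60 ms from baseline (Visit 2").

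**The concern.** The replicate recordings are made at a visit that normally does not supply the baseline. The error in the one Visit 2 reading is shared by all of a patient's changes, so a low reading raises the whole series and can move the patient into a higher maximum-change category. Averaging four cycles within an ECG reduces beat-to-beat noise only. It does not reduce differences between recordings or between days.

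QTc prolongation and conduction disorders are listed class effects (Protocol 1.2 and 1.4.2), and SAP 7.4.1 says the Phase 3 dose choice will weigh safety. What is at stake is the precision of the ECG summaries and the number of patients in each arm who appear above 30 ms by noise alone. The visible text gives no reason for leaving the triplicate out and plans no sensitivity analysis with an averaged baseline.

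**Working it through.** The documents contain no QTcF variance, expected count or ECG power, so there is no planned figure to reproduce.

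**Inputs.** From the documents: three ECGs at Visit 1, one at Visit 2, 15 single ECGs afterwards, and 60 patients per arm. Assumed: total within-patient SD *s* of one ECG of 8, 10 or 12 ms; share *f* of that variance arising between ECGs of the same session, central value 0.5.

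**Variance of change at one visit.**
- Single Visit 2 baseline: s² + s² = 2s².
- Mean of the Visit 1 triplicate average and Visit 2: the Visit 1 average has variance s²[(1−f) + f/3] and Visit 2 has s². The baseline variance is one quarter of their sum, s²(0.5 − f/6), so the change has variance s²(1.5 − f/6).
- f = 0.5: 1.417/2 = 0.708, or 29% lower. f = 0.25: 1.458/2 = 0.729, 27% lower. f = 0.75: 1.375/2 = 0.688, 31% lower.

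At s = 10 and f = 0.5, the standard error of an active-minus-placebo difference in mean change at one visit (60 per arm) is √(2 × 200/60) = 2.58 ms now and √(2 × 141.7/60) = 2.17 ms with averaging.

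**Drift before Visit 2.** Individual drift of SD *d* at Visit 1 adds d²/4 to the variance. With d = 8 ms this is 16 ms²:
- s = 8: (90.7 + 16)/128 = 0.83, 17% lower.
- s = 10: (141.7 + 16)/200 = 0.79, 21% lower.
- s = 12: (204 + 16)/288 = 0.76, 24% lower.

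**Patients with a maximum QTcF increase above 30 ms.** Simulation of 400,000 patients, f = 0.5, 15 independent on-treatment ECGs, no drift. The z value is the difference in proportions divided by its standard error with 60 per arm.

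| SD (ms) | Baseline | No effect | 5 ms effect: active minus placebo | z |
|---|---|---|---|---|
| 8 | Visit 2 | 4.0% | 7.2 points | 1.5 |
| 8 | Averaged | 1.1% | 4.2 points | 1.3 |
| 10 | Visit 2 | 13.4% | 11.6 points | 1.6 |
| 10 | Averaged | 7.0% | 11.2 points | 1.9 |
| 12 | Visit 2 | 24.9% | 12.8 points | 1.5 |
| 12 | Averaged | 18.1% | 15.2 points | 1.9 |

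At SD 10 the no-effect figures are about 8 and 4 patients per arm of 60.

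**Which source is larger.** At SD 10 with the Visit 2 baseline, noise takes 1.7% of patients above 30 ms at any one visit, but 13.4% on the maximum of 15. Averaging the baseline brings 13.4% down only to 7.0%. The maximum over many single ECGs is therefore the larger source.

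**Above 60 ms.** Noise alone gives less than 0.3% under either baseline at all three SDs.

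**The case against.** The planned rule is a stated and consistent convention. Protocol 7.2.1 sets the last pre-dose value as the general baseline for efficacy and safety, the SAP repeats it, and Visit 2 is also the reference in the protocol's discontinuation criterion. The triplicate falls at the visit where the 450 ms entry limit is judged (Protocol 3.3.3). Safety analyses are descriptive, so no test is affected. SAP 7.8.4 also plans absolute QTcF thresholds, a shift table and a plot of maximum change against baseline. All of this stands, and it limits the weight of the point.

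A reader might infer that the noise hides a real difference between doses. The documents do not support that. The noise is the same in kind in every arm and a placebo arm is shown beside the doses. With a 10 ms effect at SD 10, about 41% of active patients against 13% on placebo would exceed 30 ms under the planned baseline. At SD 8 the averaged baseline gives a slightly weaker above-30 ms contrast, because the counts become small. It would also be wrong to infer that averaging removes the false counts.

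Two further objections stand in part. Visit 1 may be 10 weeks or more before Visit 2; drift of 8 ms reduces the gain but does not remove it. An averaged baseline used alone would also part from the protocol's reference: a patient stopped for a rise measured from Visit 2 could be missing from the above-60 ms table.

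**Conclusion.** The point holds as a loss of precision. Using ECGs already collected lowers the variance of change by about 29% with an equal within/between-visit split, and by 17-24% with 8 ms of drift at Visit 1. The contrast in mean change is sharper in every scenario examined. Noise-only counts above 30 ms fall in every arm, for example from about 13% to 7% at SD 10 ms.

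The comparison with placebo is diluted, not biased, provided the number of ECGs per patient is similar across arms; more early discontinuation on active drug would lower the maximum there. By z value, the above-30 ms contrast improves at SD 10-12 ms and not at 8 ms. Counts above 60 ms are essentially unaffected. All sizes rest on assumed SDs, an assumed variance split and independent on-treatment readings. The direction of the variance result does not depend on the SD or the split if there is no drift.

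**What to change.** In SAP 6.7, define the analysis baseline for QTcF, QT, HR, PR and QRS as the mean of two values, the Visit 1 triplicate average and the Visit 2 pre-dose ECG, using whichever exists if only one is available. Use it in SAP 7.8.4 for the change summaries and the maximum-change categories. Also show the categorical tables and the change-based notable findings against the Visit 2 value, so that they remain traceable to the reference in Protocol 3.3.4.1. Nothing in the protocol's criterion is changed by this.

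The cost is SAP wording and one extra set of tables, with no new visits or recordings. If the database is already locked, add the averaged-baseline tables as supportive. There are two small downsides. Visit 1 can be 10 or more weeks earlier than Visit 2. The 450 ms entry limit at Visit 1 also lowers the averaged baseline by about 0.2 to 0.3 ms (assuming a mean QTcF of 415-420 ms and a between-patient SD of 18-20 ms).
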